14. METHOD OF STATISTICAL ANALYSIS

Descriptive summary of patient demographics and disease characteristics will be presented for all enrolled population and the evaluable population.

14.1 Primary Objective

The concordance rate, sensitivity, specificity, positive and negative predictive values and their exact 2-sided 95% confidence interval for comparing mutation status between tumour and plasma samples will be calculated for evaluable population for Europe and Japan.

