Non-Interventional Study (NIS) ProtocolNIS Name/CodeD7913C00070Edition NumberFinal 3.0Date

A diagnostic Study of European and Japanese advanced NSCLC patients to evaluate suitable sample types for EGFR testing: The ASSESS Study

Sponsor:

AstraZeneca AB, [name]

A diagnostic Study of European and Japanese advanced NSCLC patients to evaluate suitable sample types for EGFR testing: The ASSESS Study

Medicinal Products (type, dose, mode of administration) and concomitant medication

The assignment of a subject to a particular therapeutic strategy is not decided in advance by a protocol but falls within current practice and marketing authorisation.

Study Rationale

This study will be conducted in Japan and Europe and will assess the concordance of *EGFR* mutation status derived from tumour samples and blood based circulating free DNA. The data generated will inform the use of less-invasive sample types in diagnostic practice. The study also aims to assess the current status of *EGFR* mutation testing across Japan and Europe and gaps in currently available data including *EGFR* mutation frequency in particular populations and demographic subgroups, *EGFR* mutation frequency in histological subtypes of NSCLC, *EGFR* mutation test process and methodology, utility of multiple sample types in the assessment of *EGFR* mutation status, and impact of *EGFR* mutation testing process, ensuring that patients have access to testing and are treated appropriately on the basis of the molecular features of their disease.

Study Objectives

(a) Primary objective

To determine the level of concordance between *EGFR* mutation status obtained via tissue/cytology and blood (plasma) based testing.

- (b) Secondary objectives
- 1. To determine the *EGFR* mutation frequency (including mutation subtypes) in patients with advanced NSCLC (aNSCLC) of adenocarcinoma and non-adenocarcinoma histologies.
- 2. To describe first line therapy choice following *EGFR* mutation testing.
- 3. To describe second line therapy choice following discontinuation of first line treatment for patients confirmed as *EGFR* mutation positive via tissue/cytology.
- 4. To summarise *EGFR* mutation testing practices in terms of methods, sample types, success rate, mutation detection rate, testing turnaround time and reasons for not testing.
- 5. To determine the correlation between *EGFR* mutation status from tumour and demographic data and disease status.

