3. SELECTION OF SUBJECT POPULATION

- Patients with locally advanced (stage IIIA/B) or metastatic NSCLC who are newly diagnosed, have not received any local or systemic chemotherapy. Locally advanced patients should not be eligible for curative treatment (including surgery and chemoradiotherapy). The tumour samples of these patients are planned to undergo EGFR mutation testing, or have had an EGFR mutation test within 2 months of screening, or
- Patients who have newly diagnosed locally advanced (stage IIIA/B) NSCLC who are not eligible for curative treatment (including surgery and chemoradiotherapy) or metastatic NSCLC and have not received systemic chemotherapy. Previous or planned palliative radiotherapy is allowed. The tumour samples of these patients are planned to undergo EGFR mutation testing, or have had an EGFR mutation test within 4 months of screening, or
- Patients who have had surgical resection with or without adjuvant chemotherapy and have experienced recurrent disease. In this case if a new/contemporary biopsy is available, it should be used for *EGFR* mutation testing. If the only sample available is a historical diagnostic/resected sample, then this may be used for *EGFR* mutation testing (no time- limit from screening).

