3.2 Inclusion criteria

The subject population that will be observed in the NIS, must fulfil all of the following criteria:

- 1. Provision of written informed consent
- 2. Patients aged 18 years and older from European countries and patients aged 20 years and older for patients from Japan
- 3. Histological or cytological confirmed locally advanced NSCLC (stage IIIA/B) not suitable for curative treatment or metastatic (stage IV) NSCLC.
- 4. Newly diagnosed patients with locally advanced and/or metastatic NSCLC who are systemic treatment Naïve (i.e. no chemotherapy or EGFR-TKI) or patients with recurrent disease who have previously received adjuvant chemotherapy (not including EGFR-TKI)
- 5. Provision of diagnostic cancer tissue or cytology sample upon inclusion (surgical specimen, biopsy sample, or cytology sample is acceptable)
- 6. Provision of a routine blood (plasma) sample

The prescription of any medicinal product is clearly separated from the decision to include the subject in the NIS.

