7.2 Secondary variables

The following data will be collected in order to fulfil the secondary objectives of the study:

Patient demographics	• Gender		
	• Age		
	• Race		
	EthnicityWHO Performance status		
	• Smoking status:		
	• Intensity (cigarettes per day)		
	o Duration (years)		
	• Time since cessation (years)		
	• Disease status:		
	 Date of first diagnosis 		
	 Histological type 		
	• TNM (AJCC) disease stage		
	(Edition 7)		
	• Number of organs with		
	metastasis		
	• Location of		
	metastasis/metastases		
1 st -line treatment decision after testing	• Name of treatment		
	• Treatment start date		
	• Reason for treatment choice (including		
and 1. () 1. () ()	Clinical Trial enrolment)		
2 nd -line treatment decision (for patients	• Name of treatment		
confirmed as EGFR mutation-positive via	• Treatment start date		
tissue/cytology)	• Reason for treatment choice (including		
	Clinical Trial enrolment)		
EGFR mutation testing endpoints	• Test result		
	• Overall mutation result (positive		
	negative, unknown)*		
	• Mutation subtype		
	 Testing methodology Sample time and envilopility 		
	• Sample type and availability		
	 Testing turnaround time Basson(a) for testing not being 		
	 Reason(s) for testing not being performed 		
Footnote:	performed		

Footnote:

Smoking is a multi-dimensional phenomenon with many characteristics, such as intensity (in cigarettes per day), duration (in years) and time since cessation (in years). In this study, every patient should report the all information list above to determine the smoking status.

- Deletion, substitution, and/or insertion mutations of tyrosine kinase domain of the *EGFR* gene will be identified and recorded in the CRF. Methods used for measuring *EGFR* mutation status should also be recorded.

*EGFR mutation status will be recorded for each patient as:

- Positive: *EGFR* mutation detected (one or more individual mutations)
- Negative: EGFR mutation not detected
- Unknown: *EGFR* mutation status not determined as *EGFR* mutation positive or *EGFR* mutation negative

It is accepted that mutation assays (methods and individual mutation assays) may differ between labs and institutions. Thus a patient can be positive or negative depending on the method used. As a minimum, laboratories should assess the common *EGFR* mutations: Exon 19 deletions, and Exon 21 L858R point mutations.

Mutation subtypes will also be recorded:

- Exon 18:
 - o G719C/S/A
 - 0 other
- Exon 19:
 - o deletions
 - o other

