8.1 Specification of biological samples

8.1.1 Pathology review

Histopathological review of tumour material should take place to ensure that samples are adequate for use. Where appropriate tissue or cytology samples should be reviewed by suitably qualified pathologist and classified according to the most recent WHO classification. Reasons for the exclusion of the material for use in subsequent analyses may include:

- 1. Inappropriate sample (i.e., provision of materials inconsistent with NSCLC)
- 2. Insufficient tumour sample
- 3. Inadequate cellular morphology (e.g., due to poor or inappropriate fixation)

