14.2 Secondary Objectives

EGFR Mutation Frequency

The *EGFR* mutation frequency from the tumour sample in the evaluable population will be summarised overall and by country/region by adenocarcinoma and non-adenocarcinoma histologies.

First line treatment choice

 1^{st} line treatment choice following *EGFR* mutation testing will be summarised descriptively for the overall evaluable population by *EGFR* mutation status, *EGFR* mutation subtype and

by country/region.

Second line treatment choice

The percentage of patients on 2^{nd} line treatment, including treatment choice following discontinuation of first line treatment for patients confirmed as *EGFR* mutation positive via tissue/cytology will be summarised descriptively for the evaluable EGFR mutation positive population by *EGFR* mutation status, *EGFR* mutation subtype and by country/region. Treatment sequence i.e. 1^{st} line treatment choice and 2^{nd} line treatment choice will be summarised descriptively.

Summaries of EGFR mutation testing practices

The testing methodology, sample type and availability, testing turnaround time, testing success rate and mutation detection rate will be summarised using appropriate descriptive statistics for evaluable population. The reasons for testing not being performed will be listed.

Correlation between EGFR mutation status from tumour sample and demographic characteristics and disease status

The patient characteristics of the enrolled population will be compared to the characteristics of the evaluable population in order using summary statistics to understand any relationship between all aNSCLC patients and those whose samples undergo *EGFR* mutation testing.

The correlation between *EGFR* mutation status and both demographic characteristics and disease status will be analysed using a multivariate logistic regression model, constructed for the evaluable population to model *EGFR* tumour mutation status at baseline (*EGFR* mutation positive versus *EGFR* mutation negative from tumour sample) and key demographic characteristics such as histology (adenocarcinoma versus non-adenocarcinoma), smoking status (never- versus eversmoker) gender (female versus male), age (≤ 65 versus 65+) and WHO performance score (PS; 0-1, 2) and key disease status characteristics (time since diagnosis, disease stage at progression and number of organs with metastasis).

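### The rationale names the utility of different sample types as a gap to assess, but no analysis stated in the protocol relates sample type to plasma agreement, test success or detection rate

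*Protocol*

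**What the plan says.** The protocol title says that the study is "to evaluate suitable sample types for EGFR testing". The Study Rationale lists the "utility of multiple sample types in the assessment of" EGFR mutation status among the gaps to be assessed.

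The tumour reference is mixed by design. In inclusion criterion 5 (section 3.2), a "surgical specimen, biopsy sample, or cytology sample is acceptable". Section 3 also admits older material in recurrent disease: "If the only sample available is a historical diagnostic/resected sample", it may be used without a time limit. Section 7.2 records sample type and test method, and concedes: "Thus a patient can be positive or negative depending on the method used".

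The stated analyses split as follows.
- Section 14.1: concordance, sensitivity, specificity, PPV and NPV "for comparing mutation status between tumour and plasma samples will be calculated for evaluable population for Europe and Japan".
- Table 4 (section 12.1): method, sample type, success rate, detection rate and turnaround time, overall and by country or region.
- Section 14.2: sample type appears in the same list as the other items, and "testing success rate and mutation detection rate will be summarised using appropriate descriptive statistics" for the Evaluable Population.

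**The concern.** Sample type is to be summarised as a variable of its own, but no stated output crosses it with anything. From the stated tables a reader would learn how many references were surgical, biopsy or cytology. The reader would not learn how often each gave a result, how often each showed a mutation, or how plasma agreed with each.

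This also affects how the primary table is read. A mutation that the reference misses and plasma finds is counted as a plasma false positive. If such cases cluster in one specimen type, the single PPV for a region depends partly on that region's specimen mix, and no stated table would show it.

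**Working it through.** **1. The plan's own figure.** Section 15 gives a 95% interval of 40-60% for 50% sensitivity with 100 mutation-positive patients. The exact interval for 50/100 is 39.8-60.2%, so the figure reproduces. Europe: 1000 × 0.10 = 100 positives. Japan: 300 × 0.30 = 90, not 100. That is a separate matter and hardly changes the interval (39.3-60.7% for 45/90).

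**2. Effect of missed mutations in the reference.** Inputs: mutation frequency p = 10% or 30% and plasma sensitivity s = 50% (section 15). Assumptions, because the protocol gives no values: plasma makes no false positives, the reference makes no false positives, reference and plasma misses are independent, and the reference detects a share r of mutated patients.

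Cells as proportions of all patients:
- plasma+ / reference+: p·s·r
- plasma− / reference+: p·(1−s)·r
- plasma+ / reference−: p·s·(1−r)
- plasma− / reference−: (1−p) + p·(1−s)·(1−r)

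Therefore:
- apparent sensitivity = psr / [psr + p(1−s)r] = s
- apparent PPV = psr / [psr + ps(1−r)] = r
- apparent specificity = [(1−p) + p(1−s)(1−r)] / [(1−p) + p(1−r)]
- concordance = (1−p) + p[sr + (1−s)(1−r)]

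Example for Europe, 1000 patients, r = 0.90: the four cells are 45, 45, 5 and 905. Sensitivity is 45/90 = 50%, PPV 45/50 = 90%, specificity 905/910 = 99.5% and concordance 950/1000 = 95%.

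| r | PPV | Specificity, p = 10% | Specificity, p = 30% | Sensitivity | Concordance, 10% / 30% |
|---|---|---|---|---|---|
| 1.00 | 100% | 100% | 100% | 50% | 95% / 85% |
| 0.95 | 95% | 99.7% | 99.0% | 50% | 95% / 85% |
| 0.90 | 90% | 99.5% | 97.9% | 50% | 95% / 85% |
| 0.80 | 80% | 98.9% | 96.1% | 50% | 95% / 85% |

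Concordance is exactly constant only because s = 50%. At s = 70% and r = 0.90 it moves from 97.0% to 0.90 + 0.10 × (0.63 + 0.03) = 96.6% at p = 10%, and from 91.0% to 0.70 + 0.30 × 0.66 = 89.8% at p = 30%. The change is small.

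**3. Effect of the mix.** Assume tissue detects 95% and cytology 80%. The pooled PPV is 0.7 × 95 + 0.3 × 80 = 90.5% with 30% cytology, and 0.5 × 95 + 0.5 × 80 = 87.5% with 50%. With cytology at 90% the values are 93.5% and 92.5%.

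**4. What a split could show.** Exact 95% intervals for a sensitivity of 50%:

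| Positives in stratum | Interval |
|---|---|
| 60 | 36.8-63.2% |
| 40 | 33.8-66.2% |
| 20 | 27.2-72.8% |

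For PPV, take 100 mutated patients, 50 of them plasma positive and 30% with a cytology reference. That is about 12/15 confirmed for cytology (exact interval 52-96%) and 33/35 for tissue (81-99%), Fisher p = 0.15.

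**5. Success rate.** Section 7.2 defines it as successful tests over tests requested. Section 14.2 computes it in the Evaluable Population, which section 13.2 evidently means to limit to patients with known tumour and plasma results. Every test in that set succeeded, so the rate is 100% in any sample type by construction.

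**The case against.** The strongest reply is that the main question is posed and answered correctly. Section 1.1 explains the suitability question as plasma against the tissue or cytology used in routine practice, and section 14.1 estimates exactly that. The phrase on multiple sample types is one item in a list in the rationale, and secondary objective 4 asks only for a summary of testing practices. This stands. A reader might infer that the study cannot answer its sample-type question. The documents do not support that: sample type is collected, nothing forbids the cross-tabulation, and an analysis plan may add it.

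A second reply is that nothing in the protocol says cytology detects fewer mutations than tissue, and section 8.1.1 has a safeguard: "Histopathological review of tumour material should take place to ensure that samples are adequate for use". This stands as to size, since the detection rates used above are assumptions. Pathology review reduces inadequate material but does not show that yields are equal.

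A third reply is that a split gives little. Strata are small, and reference type may go with local assay, country or histology, so a difference could not be attributed to specimen type alone. This also stands, and it limits the tables to description.

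The replies do not remove the mismatch between a named aim and the stated splits. The protocol names breakdowns where it wants them: mutation frequency by histology, treatment by mutation status and subtype, and plasma against tumour detection within demographic and disease subgroups. Sample type is not among them.

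**Conclusion.** The point holds as a modest improvement. The protocol names the utility of sample types as something to assess and collects the variable, yet fixes its splits as Europe and Japan for accuracy and as overall and country or region for testing practice. No analysis stated in it uses sample type to address that aim. The primary objective is not undermined.

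A reader might also infer that weak references are charged to plasma across all the accuracy measures. They are not. With independent errors, missed mutations in the reference lower PPV, and specificity slightly. They leave sensitivity, the measure that sizes the study, unchanged, and concordance unchanged or nearly so. The direction for PPV rests on the independence and no-false-positive assumptions, and the size rests on detection rates that the protocol does not give. If both tests miss the same tumours, apparent sensitivity would rise instead. False positives in the reference would act differently again: with 1% of them, apparent sensitivity falls to 45.9% at 10% frequency and 48.9% at 30%.

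**What to change.** - **Section 14.1:** add supportive 2x2 tables with exact 95% intervals by tumour reference type (tissue versus cytology) within each region. Keep the pooled regional analysis as primary.
- **Section 14.2 and Table 4:** report detection rate, turnaround time and success rate by sample type (surgical, biopsy, cytology, plasma).
- **Success rate:** compute it on all tests requested in the Enrolled Population, using the section 7.2 denominator. Splitting it within the Evaluable Population would give 100% everywhere.

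The cost is a few extra tables from data already collected. The strata will have wide intervals, and reference type may be confounded with local assay, so the tables should be labelled descriptive and not used to rank specimen types.

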14.2 Secondary Objectives

EGFR Mutation Frequency

The *EGFR* mutation frequency from the tumour sample in the evaluable population will be summarised overall and by country/region by adenocarcinoma and non-adenocarcinoma histologies.

First line treatment choice

 1^{st} line treatment choice following *EGFR* mutation testing will be summarised descriptively for the overall evaluable population by *EGFR* mutation status, *EGFR* mutation subtype and

by country/region.

Second line treatment choice

The percentage of patients on 2^{nd} line treatment, including treatment choice following discontinuation of first line treatment for patients confirmed as *EGFR* mutation positive via tissue/cytology will be summarised descriptively for the evaluable EGFR mutation positive population by *EGFR* mutation status, *EGFR* mutation subtype and by country/region. Treatment sequence i.e. 1^{st} line treatment choice and 2^{nd} line treatment choice will be summarised descriptively.

Summaries of EGFR mutation testing practices

The testing methodology, sample type and availability, testing turnaround time, testing success rate and mutation detection rate will be summarised using appropriate descriptive statistics for evaluable population. The reasons for testing not being performed will be listed.

Correlation between EGFR mutation status from tumour sample and demographic characteristics and disease status

The patient characteristics of the enrolled population will be compared to the characteristics of the evaluable population in order using summary statistics to understand any relationship between all aNSCLC patients and those whose samples undergo *EGFR* mutation testing.

The correlation between *EGFR* mutation status and both demographic characteristics and disease status will be analysed using a multivariate logistic regression model, constructed for the evaluable population to model *EGFR* tumour mutation status at baseline (*EGFR* mutation positive versus *EGFR* mutation negative from tumour sample) and key demographic characteristics such as histology (adenocarcinoma versus non-adenocarcinoma), smoking status (never- versus eversmoker) gender (female versus male), age (≤ 65 versus 65+) and WHO performance score (PS; 0-1, 2) and key disease status characteristics (time since diagnosis, disease stage at progression and number of organs with metastasis).

Correlation between *EGFR* mutation status derived from plasma sample and demographic characteristics and disease status

The *EGFR* mutation status from plasma sample and demographic and disease characteristics will be summarised for the evaluable population with available samples. This summary will be compared with summaries of the *EGFR* mutation status from tumour samples within the same demographic and disease status characteristics to understand any patterns of differences in the mutation detection rate in the plasma sample within key patient sub-groups.

The correlation between *EGFR* mutation status from plasma sample and both demographic characteristics and disease status will be analysed using a multivariate logistic regression model, constructed for the evaluable population to model *EGFR* tumour mutation status at baseline (*EGFR* mutation positive versus *EGFR* mutation negative from tumour sample) and key demographic characteristics such as histology (adenocarcinoma versus non-adenocarcinoma), smoking status (never- versus eversmoker) gender (female versus male), age (≤ 65 versus 65+) and WHO performance score (PS; 0-1, 2) and key disease status characteristics (time since diagnosis, disease stage at progression and number of organs with metastasis).

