1.2 Secondary objectives

Secondary objectives of the study are:

- 1. To determine the *EGFR* mutation frequency (including mutation subtypes) in patients with advanced NSCLC (aNSCLC) of adenocarcinoma and non-adenocarcinoma histologies.
- 2. To describe first line therapy choice following *EGFR* mutation testing.
- 3. To describe second line therapy choice following discontinuation of first line treatment for patients confirmed as *EGFR* mutation positive via tissue/cytology.
- 4. To summarise *EGFR* mutation testing practices in terms of methods, sample types, success rate, mutation detection rate, testing turnaround time and reasons for not testing.
- 5. To determine the correlation between *EGFR* mutation status from tumour and demographic data and disease status.
- 6. To determine the correlation between *EGFR* mutation status derived from plasma (blood) and demographic data and disease status.

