13.2 Evaluable Population

The Evaluable Population consists of all enrolled patients with all non-missing or unknown:

- Tumour sample *EGFR* mutation test status.
- Tumour sample *EGFR* mutation test sub-type.
- Plasma *EGFR* mutation test status.
- Plasma *EGFR* mutation test sub-type.

Unless otherwise specified all summaries will be based on the Evaluable Population.

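### Uncommon EGFR sub-type frequencies are understated wherever local tumour assays do not cover them, because patients not tested for a sub-type stay in the denominator

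*Protocol*

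**What the plan says.** Secondary objective 1 (Protocol Section 1.2) is the EGFR "mutation frequency (including mutation subtypes) in patients with advanced NSCLC (aNSCLC) of adenocarcinoma and non-adenocarcinoma histologies". For its analysis, Section 14.2 states that the "mutation frequency from the tumour sample in the evaluable population will be summarised overall and by country/region by adenocarcinoma and non-adenocarcinoma histologies". That sentence does not name sub-types. Their denominator comes from Section 13.2: "Unless otherwise specified all summaries will be based on the Evaluable Population". Membership of that set depends on known tumour and plasma results, not on what the assay was able to detect.

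On the assay, Section 7.2 says: "As a minimum, laboratories should assess the common *EGFR* mutations: Exon 19 deletions, and Exon 21 L858R point mutations". It also says "It is accepted that mutation assays (methods and individual mutation assays) may differ between labs and institutions" and draws the consequence: "Thus a patient can be positive or negative depending on the method used". The coding rule is "Negative: EGFR mutation not detected". The recorded sub-types go well beyond the minimum and include G719C/S/A, T790M, exon 20 insertions, S768I, L861Q and other categories. The test method is recorded, but Section 7.2 does not ask which of these sub-types each assay covered.

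Under Section 8, European tumour tests are run in mixed local laboratories (academic, hospital, commercial). Japanese tumour tests are run at a commercial laboratory.

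**The concern.** A sub-type frequency needs a denominator of patients in whom that sub-type could have been found. Here a patient tested only for exon 19 deletions and L858R who carries, for example, L861Q alone is recorded as Negative rather than Unknown. The patient stays in the Evaluable Population and adds to the denominator for L861Q without any chance of adding to the numerator.

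The study rationale lists EGFR mutation frequency in particular populations among the data gaps to be filled. Two regions with the same biology but different assay menus would show different frequencies of the uncommon sub-types, and the tables would not separate the two explanations. The Europe–Japan contrast is the most exposed, because region and type of laboratory go together. The issue concerns the tumour sample alone and does not depend on how tumour–plasma agreement is analysed.

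**Working it through.** **Inputs from the Protocol (Section 15).** Europe: 1000 patients, true frequency p = 10%. Japan: 300 patients, p = 30%.

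**The plan's own figures.** Europe: 1000 × 0.10 = 100 positives, as stated. Japan: 300 × 0.30 = 90, where the Protocol states 100; nothing below depends on that difference.

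**Assumed inputs (not in the documents).** s = share of true positives whose mutation lies outside the minimum menu, 5–20%. c = share of evaluable patients in a region whose assay covers it, 0–100%. Coverage is taken as unrelated to mutation status within a region.

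**Formulas.**
- Uncommon frequency, all evaluable patients as denominator: p × s × c
- Uncommon frequency, covered patients only: p × s (for c > 0)
- Total frequency as detected: p × (1 − s) + p × s × c
- Exon 19 deletions plus L858R: p × (1 − s), free of c

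The ratio of the first to the second is c, so the relative understatement is 1 − c whatever p and s are.

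**Uncommon frequency at s = 10%.**

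| c | Europe, as planned | Europe, covered only | Japan, as planned | Japan, covered only |
|---|---|---|---|---|
| 100% | 1.00% | 1.00% | 3.00% | 3.00% |
| 75% | 0.75% | 1.00% | 2.25% | 3.00% |
| 50% | 0.50% | 1.00% | 1.50% | 3.00% |
| 25% | 0.25% | 1.00% | 0.75% | 3.00% |
| 0% | 0% | not estimable | 0% | not estimable |

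Exon 19 deletions plus L858R stay at 9.0% in Europe and 27.0% in Japan in every row.

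**Total frequency by country.** Take two countries with p = 10%, one fully covered (c = 1) and one at the minimum menu (c = 0). The spurious difference is p × s:
- s = 5%: 10.0% against 9.5%
- s = 10%: 10.0% against 9.0%
- s = 15%: 10.0% against 8.5%
- s = 20%: 10.0% against 8.0%

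For scale, an equal split of 1000 patients over seven European countries gives about 143 each. With 14/143 positive, the exact 95% CI is 5.5–15.9%.

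**Pooling covered patients across regions.** Assume s = 10%, c = 25% in Europe and 100% in Japan.
- True: (1000 × 0.10 × 0.10 + 300 × 0.30 × 0.10)/1300 = (10 + 9)/1300 = 1.46%
- As planned: (2.5 + 9)/1300 = 11.5/1300 = 0.88%, 39% too low
- Covered patients pooled: 11.5/(250 + 300) = 11.5/550 = 2.09%, 43% too high
- Regional estimates weighted to regional sample size: (1000 × 2.5/250 + 300 × 9/300)/1300 = (10 + 9)/1300 = 1.46%

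Pooling overshoots because the well-covered region is also the one with the higher frequency. Weighting removes this.

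**The case against.** The strongest reply is that the Protocol does not spell out a sub-type denominator. The Section 14.2 sentence and the matching row of Table 4 omit sub-types, Section 13.2 leaves room for exceptions, and a SAP not shown here may define the tables. This stands in part: the denominator is a default, not an explicit sub-type rule. But it is the rule that applies unless something overrides it. A SAP also cannot restrict to covered patients if coverage was never collected and the method name does not reveal the menu.

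Second, this is a non-interventional, descriptive study of routine testing. It openly accepts assay differences and will summarise test methods by country/region. Frequency as detected in practice is a legitimate quantity. That also stands, provided the figure is labelled as such; it is not the sub-type frequency in patients that objective 1 names.

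A reader might infer three stronger things, none of which the documents support:
- That total frequencies by country are seriously distorted. The extreme contrast gives 0.5–2.0 points, small beside a single-country interval of 5.5–15.9%. Sub-type counts by country would be very small on any denominator: 10 uncommon positives over seven countries is fewer than two each.
- That the histology comparison is distorted. This would need coverage, or the uncommon share, to differ between adenocarcinoma and non-adenocarcinoma, and nothing in the Protocol says so.
- That pooling covered patients is a sufficient remedy. The example above shows that it can overshoot.

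**Conclusion.** The concern holds for the uncommon sub-types. Where some laboratories use narrow menus, which the Protocol permits, the default denominator understates each uncommon sub-type's frequency within a region by a relative (1 − coverage). This rests on coverage being unrelated to mutation status in that region. The actual size cannot be derived: coverage could be near complete, in which case the effect is negligible, and the uncommon share is not given either. Exon 19 deletion and L858R frequencies are unaffected if every laboratory meets the minimum menu. The effect on total frequency is modest. The change is worth making because sub-types are expressly part of objective 1 and the remedy is cheap.

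**What to change.** In Section 14.2:

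1. Report the frequency of exon 19 deletions plus L858R as the comparable figure across country/region. Give any-mutation frequency as a second figure, labelled as detected by the local assay.
2. Report each uncommon sub-type's frequency among patients whose local assay covered it, by region. Form any overall figure by weighting the regional estimates to the regional sample sizes, not by pooling covered patients. Where no patient in a region was covered, state that the frequency is not estimable.
3. Add an eCRF field, covered / not covered, for each listed sub-type, because the method name may not identify the menu.

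Item 1 needs no new data. Items 2 and 3 cost one extra data field and wider intervals for the uncommon sub-types: at 25% coverage in Europe, for example, the denominator falls from 1000 to 250. Those intervals reflect how many patients were actually tested for the sub-type.
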